This study is a prospective double-blinded randomized controlled study that will be done at two sites: Johns Hopkins Bayview Medical Center and Greater Baltimore Medical Center. Female patients over 18 years of age, who present for treatment of painful bladder syndrome (IC/PBS) at the Pelvic Floor Center at the Johns Hopkins Bayview Medical Center, will be considered for inclusion in the study (please see below for inclusion and exclusion criteria). The primary investigator and co-investigators will determine patient eligibility. The patients will be asked to participate in the study if they are undergoing cystoscopy with hydrodistention for a presumed diagnosis of IC/PBS. When the patient presents to the operating room on the day of their scheduled surgery they will be asked to complete the PUF questionnaire, the interstitial cystitis symptom and problem index, and the Visual Analog Scale (VAS). This time point has been chosen to minimize the temporal variation seen in pain. Patients will be randomized to either preemptive bilateral pudendal nerve block with either 20 cubic centimeters 1% lidocaine or 20 cubic centimeters normal saline after anesthesia induction, participants will be stratified by type of anesthesia. The circulating nurse will be provided with a sealed opaque envelope with the patient group allocation and he/she will provide the operating surgeon with the study drug in a syringe labeled "pudendal nerve block". The placement of the pudendal nerve block will be performed in a standardized fashion per protocol. The patients will receive their standardized anesthetic regiment per anesthesiology guidelines. At the conclusion of the case the patients will be monitored in the postoperative anesthesia unit for recovery per nursing guidelines. The patients will be asked to rate their pain on a 100mm VAS, the O'Leary Sant, and the PUF at 2 hours postoperatively.

- b. Study duration and number of study visits required of research participants.

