The interstitial cystitis symptom index and the problem index and PUF questionnaire and VAS will be repeated at 2 hours, 2 weeks, 6 weeks and 3 months postoperatively via a telephone interview. These time points have been specifically chosen due to their common use as intervals for assessing pain. Additionally, the expected difference in pain intensity for these time intervals is well described in the literature¹⁷. Furthermore, the mean duration of action of cystoscopy with hydrodistention is reported to last between 2 and 6 weeks, and we will be certain to capture evidence of prolonged efficacy if study follow up is extended to 3 months post operatively^{17, 18, 19}.

- c. Blinding, including justification for blinding or not blinding the trial, if applicable.

Randomization to 1% Lidocaine versus placebo will be performed using computer or hand generated 1:1 block permutations and stratified by anesthesia type. Assignment will be revealed in the operating room after the patient receives anesthesia. We will randomize 120 patients total (60 at each site, 30 for placebo and 30 for treatment).

- d. Justification of why participants will not receive routine care or will have current therapy stopped.

Currently, hydrodistention is routinely done without pudendal nerve block. This study will introduce an addition to standard care that may alleviate postoperative pain.

- e. Justification for inclusion of a placebo or non-treatment group.

This study requires a placebo as this will allow for a comparison group, will enable us to account for a placebo effect and potential bias. However, both groups will be receiving standard treatment, which is hydrodistention.

- f. Definition of treatment failure or participant removal criteria.

Participants may be removed from the study if they are diagnosed/newly recognized to meet any of the exclusion criteria, including intolerance of local anesthesia, new bleeding disorder, or new onset mental status change that precludes the patient from being able to follow instructions or accurately assess pain control.

- g. Description of what happens to participants receiving therapy when study ends or if a participant's participation in the study ends prematurely.

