The PUF questionnaire is a commonly used measure for evaluating patients suspected of having IC/PBS. Its domains address what are considered the hallmarks of the disease, namely pain, urinary urgency, and frequency of urination³². Parsons et al. initially examined the value of the PUF questionnaire as a predictive diagnostic tool in 2002. In this study, a direct correlation was found between greater PUF scores and the likelihood of a positive PST in patients with suspected IC/PBS and gynecologic pain³³. Since then the PUF questionnaire has been considered a valid diagnostic screening tool for patients with possible IC/PBS and will be the tool used in this study for that purpose.

c. Statistical plan including sample size justification and interim data analysis.

Recent evidence suggests a significant difference in 2-hour postoperative mean VAS scores after preemptive analgesia with 1% lidocaine (50.1 ± 27.9) compared to placebo (70.6 ± 22.6)³⁴. Based on this estimated mean difference we are planning this study with 50 participants ($n = 50$). The Type I error probability associated with the test of this null hypothesis is 0.05, with a power of 80%. Demographic, surgical, and clinical outcomes will be assessed using t-test, chi squared, and Fisher exact tests where appropriate. For continuous measures, normally distributed data will be compared with Students t test; non-normally distributed data will be compared with Wilcoxon test. Visual analog pain scores will be compared using repeated measures of variance. Furthermore, an intention to treat analysis will be performed for the participants who drop out prior to study completion.

d. Early stopping rules.

- e. Participants who no longer wish to be a part of the study may stop without penalty at any time during the study.

8. Risks

- a. Medical risks, listing all procedures, their major and minor risks and expected frequency.

There is minimal risk involved in performing pudendal nerve blocks, these risk include a less than 1% chance of additional pain, bleeding, hematoma or lidocaine systemic toxicity.

- b. Steps taken to minimize the risks.

In order to minimize risk the pudendal nerve block will be performed by a trained urogynecologist in the operating room, additionally the patients will be monitored by an anesthesiologist during the procedure for any signs of systemic toxicity.

The participants will also be monitored in the postoperative recovery area for 2 hours after their procedure.

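### Section 7c justifies 50 participants at 80% power, but section 4c randomizes 120; nothing links the two totals, and at 120 the stated power is wrong.

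*Combined protocol and SAP*

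**What the plan says.** Section 7c takes its planning values from a cited study of 2-hour VAS scores, "1% lidocaine (50.1 ± 27.9) compared to placebo (70.6 ± 22.6"), and continues: "Based on this estimated mean difference we are planning this study with 50 participants". It then gives the error rates: "The Type I error probability associated with the test of this null hypothesis is 0.05, with a power of 80" percent. It does not say whether the test is one- or two-sided, and it gives no dropout rate. Dropouts appear only in a remark that an intention-to-treat analysis will be performed.

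Section 4c specifies allocation by "computer or hand generated 1:1 block permutations and stratified by anesthesia type" and sets the total: "We will randomize 120 patients total (60 at each site, 30 for placebo and 30 for treatment"). Section 4a confirms that the study "will be done at two sites: Johns Hopkins Bayview Medical Center and Greater Baltimore Medical Center", so the 120 is two sites times two arms times 30, or 60 per arm.

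Aim 1 in section 2 defines the primary comparison as one between-arm difference in mean VAS at 2 hours. Although the heading of 7c asks for interim analysis, none is described. The early stopping item (7d and 7e) covers only voluntary withdrawal by participants.

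**The concern.** The two totals differ by a factor of 2.4, and no sentence explains how one leads to the other. The 80% power can describe only one of them.

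Three things are at stake.

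- **Justification for exposure.** If the trial follows section 4c, 120 − 50 = 70 women are randomized beyond the number that 7c justifies, half of them (35) to a saline injection. Section 8a lists the risks of the block procedure, although it puts them below 1%.
- **The analysis point.** With one total in the statistical plan and another in the randomization text, the point at which the primary test is done is not fixed. The text leaves room to test at 50 and carry on to 120 if the result is not significant, and no interim plan would control the error rate.
- **Interpretation.** A reader of the results could not tell whether stopping at 50 was completion or early termination, or whether 120 was over-enrolment.

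**Working it through.** **Inputs (section 7c unless noted)**

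- Means 50.1 and 70.6 mm; difference 70.6 − 50.1 = 20.5 mm.
- SDs 27.9 and 22.6; pooled SD = √((27.9² + 22.6²)/2) = 25.39 mm.
- Standardized difference = 20.5/25.39 = 0.807.
- Alpha 0.05, power 80%; two-sided assumed because sidedness is not stated.
- Allocation 1:1 (section 4c).

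**Step 1: reproduce the plan's 50**

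Normal approximation: n per arm = 2 × (1.96 + 0.8416)² × 25.39² / 20.5² = 24.08, rounded up to 25. The total is 50, which matches 7c. A one-sided test gives 38, so the two-sided reading is the one that fits. The exact t calculation needs 26 per arm (52 in total), so 50 falls just short of 80%. The 50 is therefore a total, and the 80% belongs to it.

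**Step 2: power at each candidate size**

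Two-sample t test, noncentrality = 20.5 / (25.39 × √(2/n)):

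| n per arm | Total | Power (t) | Power (normal) |
|---|---|---|---|
| 25 | 50 | 79.9% | 81.5% |
| 30 | 60 | 86.8% | 87.8% |
| 50 | 100 | 97.9% | 98.1% |
| 60 | 120 | 99.2% | 99.3% |

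Using the larger SD of 27.9 throughout, 60 per arm still gives 97.9% (t).

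**Step 3: difference detectable with 80% power**

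At 25 per arm it is 20.5 mm (t). At 60 per arm it is 13.1 mm (t), or (1.96 + 0.8416) × 25.39 × √(2/60) = 13.0 mm by the normal approximation.

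**Step 4: can the two totals be reconciled?**

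- *50 evaluable out of 120 randomized.* Loss needed = 1 − 50/120 = 58%. The primary endpoint is taken 2 hours after surgery, while participants are monitored in recovery (section 8b). A 20% loss would give 50/0.8 = 62.5, or 63.
- *50 per arm, raised by 20%.* 50 × 1.2 = 60 per arm gives 120, but power at 50 per arm is 97.9%, not 80%.
- *50 per site, raised by 20%.* 50 × 1.2 = 60 per site gives 120. The 80% is then the power within one site before inflation. The plan states neither the 20% nor any site-level hypothesis, and Aim 1 is a single comparison across sites, for which power is 98 to 99%.

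**Step 5: two looks, if both targets were used**

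The test statistics at 50 and 120 correlate at √(50/120) = 0.645. Under no effect, with each test at two-sided 0.05, the bivariate normal probability of rejecting at least once is 0.086.

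**The case against.** **No calculation is wrong.** The 50 and the 80% agree, and 2 × 60 = 120. This is correct: the fault is an inconsistency between sections. It still leaves the 80% untrue of the trial described in 4c.

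**The per-site reading fits exactly.** If 50 is the number per site, 80% is the right per-site power and a 20% allowance gives precisely the split in 4c. The 98 to 99% is pooled power, a different quantity, so it does not by itself refute this reading. What defeats it is that the documents contain no site-level aim, no site-level analysis and no inflation factor. It may be how 120 arose, but the plan does not say so.

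**Section 4c is the operational instruction, and 50 may be leftover text.** The page header before section 7 is dated 4/14/2014, and the first page 01/08/2015. That suggests an older section 7 but does not establish which number governs.

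**The type I error scenario is hypothetical.** No passage plans a look at 50 followed by continuation. The 8.6% shows what the text leaves open; it is not a property of a stated procedure.

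**Neither total is underpowered for 20.5 mm, and both arms receive hydrodistention.** This also stands. The harm is an unjustified number and an unfixed analysis point, not a weak primary test.

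**The figures assume a two-sample t test, while 7c says VAS scores will be compared by a repeated measures analysis.** That is a fair limit. The two-mean comparison is, however, the one that reproduces the plan's own 50.

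**Conclusion.** The concern holds. Sections 4c and 7c give different totals in current text, 120 and 50, and nothing in the documents reconciles them. The 80% power is right for 50 (79.9%) and wrong for 120 (99.2%). At 120 the design has 80% power for about 13.1 mm, a difference that the plan nowhere discusses. The gap is 70 participants.

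These figures rest on the plan's means and SDs, equal allocation, a two-sided 0.05 t test on the 2-hour VAS, and complete data. The 8.6% additionally assumes two unadjusted tests, at 50 and 120. Which total the sponsor intends cannot be settled from the documents. Because the total governs both enrolment and the timing of the primary test, it must be corrected.

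**What to change.** State one total in both 4c and 7c.

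- **If 120 is intended:** rewrite 7c for 120 (60 per arm), with about 99% power for 20.5 mm or 80% power for about 13 mm at SD 25.4, two-sided 0.05. Say why 120 was chosen. If the reason is site-level power, dropout or the secondary aims, write down the assumption and its figure, since power worked back from a chosen number is not a justification on its own.
- **If 50 is intended:** change 4c to 50 in total, 25 per arm, with a matching site split. Twenty-five per site cannot be divided equally between arms; 52 (26 per site, 13 per arm at each site) can, and it also brings the exact t-test power to 81.5%.

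In either case, state the sidedness of the test and any dropout allowance, and add that the primary analysis is done once, when the stated number has been reached.

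The cost is a wording amendment to two sections. No extra patients are needed, apart from two if 52 is preferred to 50.

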Date: 01/08/2015

Principal Investigator: [name]

Application Number: IRB00034476

NCT: 02517996

Title:

Use of Preemptive Pudendal Nerve Block Prior to Hydrodistention for the Treatment of Interstitial Cystitis/Painful Bladder Syndrome (IC/PBS)

Date: 1-8-15

Principal Investigator: [name]

Application Number: IRB00034476

JHM IRB - eForm A – Protocol

- Use the section headings to write the JHM IRB eForm A, inserting the appropriate material in each. If a section is not applicable, leave heading in and insert N/A.
- When submitting JHM IRB eForm A (new or revised), enter the date submitted to the field at the top of JHM IRB eForm A.

1. Abstract

- a. Provide no more than a one page research abstract briefly stating the problem, the research hypothesis, and the importance of the research.

Interstitial cystitis/Painful bladder syndrome (IC/PBS) is a chronic debilitating condition that severely impacts between 2.7 and 6.5 percent of women in the United States. Despite its public health importance the pathogenesis of IC/PBS is not well understood and there is no consensus on the optimal treatment approach for this condition. Hydrodistention is the most commonly used therapy for this condition; but it is limited by severe immediate postoperative bladder pain and its short duration of action. It has been postulated that hydrodistention works by disrupting the sensory nerves within the bladder that may be contributing to bladder pain. Recent evidence has provided support for the use of preemptive pudendal nerve block as a way to blunt immediate postoperative pain. We hypothesize that preemptive pudendal nerve block prior to hydrodistention will result in lower postoperative pain after hydrodistention compared to placebo. This is a prospective double- blinded randomized study and patients will be randomized to receive preemptive bilateral pudendal nerve block with either 1% lidocaine or placebo. Bladder pain will be compared at baseline, 2 hours, 2 weeks, 6 weeks and 3 months using the Visual Analog Scale, O’Leary-Sant questionnaire and the Pelvic Pain Urgency and Frequency questionnaire.

2. Objectives (include all primary and secondary objectives)

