Our overall goal is to determine the change in bladder symptoms after preemptive pudendal nerve block before hydrodistention in patients with IC/PBS. In order to effectively characterize our outcomes we have chosen different validated instruments to assess post-operative pain. First, in order to objectively quantify pain intensity we will determine the mean difference in postoperative pain at 2 hours in the treatment group (1% Lidocaine) compared to the placebo group (saline) using the Visual Analog Scale (VAS); this will serve as our primary endpoint (AIM 1). In order to capture the most important voiding and pain symptoms and to assess the degree of bother between the two groups we will measure mean difference in interstitial cystitis symptom index and the problem index (O’Leary-Sant) and in the Pelvic pain, Urgency and Frequency (PUF) questionnaire at baseline, 2 hours, 2 weeks, 6 weeks and 3 months after treatment with hydrodistention and preemptive pudendal nerve block compared to hydrodistention with placebo (AIM 2). Finally in an attempt to expand our knowledge about the change in bladder symptoms over time, we will measure the change in the interstitial cystitis symptom index and the problem index (O’Leary-Sant) and in the Pelvic pain, Urgency and Frequency (PUF) questionnaire at baseline, 2 hours, 2 weeks, 6 weeks and 3 months

after treatment (AIM3). With this project we propose a novel approach to decreasing the immediate postoperative pain and possibly prolonging the efficacy of this intervention for the management of IC/PBS.

Aim 1. To determine the mean difference in pain at 2 hours postoperatively in patients undergoing hydrodistention with preemptive pudendal nerve block (1% Lidocaine) compared to hydrodistention with placebo (saline) using the visual analog scale (VAS).

AIM 2. To determine the mean difference in interstitial cystitis symptom index and the problem index (O'Leary-Sant) and in the Pelvic pain, Urgency and Frequency (PUF) questionnaire at baseline, 2 hours, 2 weeks, 6 weeks and 3 months after hydrodistention with preemptive pudendal nerve block (1% Lidocaine) compared to hydrodistention with placebo (saline).

AIM 3. To measure the change in the interstitial cystitis symptom index and the problem index (O'Leary-Sant) and in the Pelvic pain, Urgency and Frequency (PUF) questionnaire at baseline, 2 hours, 2 weeks, 6 weeks and 3 months after treatment with hydrodistention with and without preemptive pudendal nerve block.

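### The plan does not say which VAS analysis decides Aim 1: the endpoint and sample size concern the 2-hour difference, but the only method assigned to VAS by name is an unspecified repeated-measures analysis

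*Combined protocol and SAP*

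**What the plan says.** - **Endpoint.** Section 2 defines Aim 1 as the mean difference in pain at 2 hours, lidocaine against saline: "using the Visual Analog Scale (VAS); this will serve as our primary endpoint (AIM 1".
- **Sample size.** Section 7c starts from 2-hour results in a cited study: "Recent evidence suggests a significant difference in 2-hour postoperative mean VAS scores after preemptive analgesia with 1% lidocaine". It gives 50.1 ± 27.9 for lidocaine and 70.6 ± 22.6 for placebo, and plans 50 participants at a type I error of 0.05 and 80% power.
- **Generic method.** Section 7c: "For continuous measures, normally distributed data will be compared with Students t test; non-normally distributed data will be compared with Wilcoxon test". This names neither the VAS nor Aim 1.
- **Method for the VAS.** The next sentence of 7c: "Visual analog pain scores will be compared using repeated measures of variance". It states no effect, no contrast, no list of times and no handling of baseline.
- **Times.** Section 1: "Bladder pain will be compared at baseline, 2 hours, 2 weeks, 6 weeks and 3 months using the Visual Analog Scale". Sections 4a and 4b confirm that VAS is collected on the day of surgery and at four postoperative times.
- **Data available for adjustment.** At baseline (section 4a) "they will be asked to complete the PUF questionnaire, the interstitial cystitis symptom and problem index, and the Visual Analog Scale (VAS". In randomization (section 4a) "participants will be stratified by type of anesthesia"; section 4c repeats the stratification.

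**The concern.** An analyst who follows section 7c could judge Aim 1 in at least three ways:

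1. a two-sample test of VAS at 2 hours;
2. a group effect averaged over five times, one of which precedes treatment;
3. a group-by-time effect.

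These answer different questions. A group effect averaged over 3 months can miss a benefit confined to 2 hours. A significant group-by-time effect says that the arm difference varies over time, not that the arms differ at 2 hours. The stated 80% power belongs only to the first. If the choice stays open until the data are seen, the 5% error rate is not protected either. Moreover, neither method in 7c is said to use baseline VAS or the anesthesia stratum, though both are already collected.

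**Working it through.** **1. Reproduce the plan's figure.** Inputs from section 7c, with each ± figure read as an SD.

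- Difference: 70.6 − 50.1 = 20.5 mm.
- Common SD: √[(27.9² + 22.6²)/2] = √644.585 = 25.39 mm.
- Normal approximation, two-sided 0.05, 80% power: n per arm = 2 × (1.960 + 0.842)² × 644.585 / 20.5² = 24.08, rounded up to 25, so 50 in total. This matches.
- Exact check: noncentrality = 20.5 / (25.39 × √(2/25)) = 2.855 on 48 df, power 79.9%.
- A one-sided test would need 19 per arm (38 in total), which does not match.

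The 50 is therefore a two-sided, two-sample comparison of means at 2 hours.

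**2. Power of the repeated-measures effects.** Assumptions not in the documents: SD 25.39 at every time, equal correlation ρ between times, five times with baseline kept, no missing data.

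- Group effect (noncentral t): a participant's mean over five times has SD = 25.39 × √[(1 + 4ρ)/5], which is 16.84, 19.67 and 20.94 at ρ = 0.3, 0.5 and 0.6. The arm difference in that mean is 20.5/5 = 4.1 mm if the benefit is at 2 hours only, and 4 × 20.5/5 = 16.4 mm if it holds at all four postoperative times.
- Group-by-time effect (noncentral F, 4 and 192 df at 25 per arm, 4 and 472 df at 60 per arm): λ = (n/2) × Σ(δⱼ − δ̄)² / [644.585 × (1 − ρ)]. For 2 hours only, Σ = 20.5² × (1 − 1/5) = 0.8 × 20.5². For a sustained benefit, Σ = 20.5² × (4 × 0.2² + 0.8²) = 0.8 × 20.5². The two are equal, so this test has the same power for both patterns and cannot tell them apart.

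Power at ρ = 0.3 / 0.5 / 0.6:

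| n per arm | Benefit | Group | Group-by-time | 2-hour t test |
|---|---|---|---|---|
| 25 | 2 hours only | 0.135 / 0.112 / 0.104 | 0.668 / 0.828 / 0.910 | 0.799 |
| 25 | sustained | 0.921 / 0.824 / 0.774 | 0.668 / 0.828 / 0.910 | 0.799 |
| 60 | 2 hours only | 0.262 / 0.205 / 0.186 | 0.978 / 0.998 / 1.000 | 0.992 |
| 60 | sustained | 1.000 / 0.995 / 0.989 | 0.978 / 0.998 / 1.000 | 0.992 |

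The 60-per-arm rows use the 120 patients of section 4c. Simulation with 20,000 trials per setting agreed within 0.01.

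**3. Error rate if the choice is left open.** With no effect, 25 per arm, five times and ρ of 0.3 to 0.7 (20,000 simulated trials per ρ), claiming success if any one of the three tests has p < 0.05 gives about 11-12% false positives against the stated 5%.

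**4. Adjusting for baseline.** With correlation r between baseline and 2-hour VAS, ANCOVA leaves residual variance 644.585 × (1 − r²). Simulated power at 25 per arm, with baseline VAS and an assumed two-level anesthesia stratum (40,000 trials), is 0.788 / 0.826 / 0.890 / 0.934 at r = 0 / 0.3 / 0.5 / 0.6, with a null rejection rate of 0.049. At 60 per arm it is at least 0.99. At r = 0 the cost against the t test is 0.799 − 0.788 = 0.011. A three-level stratum gave a similar cost.

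**The case against.** The plan can be read coherently. Section 2 fixes one variable, one time and one contrast. In 7c the hypothesis being powered is plainly the 2-hour difference, and 2-hour VAS is a continuous measure, so the t-test or Wilcoxon sentence can be its test, with repeated measures for the time course. No sentence says that an omnibus effect decides Aim 1, and a 2-hour contrast within the repeated-measures model is not excluded. The lowest power figures need both the least natural choice of effect and a benefit gone by 2 weeks, whereas the protocol also hopes for prolonged benefit. Adjustment for baseline is a preference: the unadjusted two-sample comparison is valid, and the sample size was calculated for it.

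Much of this stands. The coherent reading is fair, and the 10-14% is not the expected outcome. But that reading is an inference. The generic sentence names neither VAS nor Aim 1, and the sentence straight after it gives VAS another method; ordinarily the specific sentence governs. A benefit confined to the early period is also not far-fetched: section 6a gives lidocaine an elimination half-life of 90-120 minutes, and section 3 predicts a smaller initial rise in pain. It is true as well that the number of anesthesia types is not given, and that the suggested model leaves out site although section 4c plans 60 patients at each.

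**Conclusion.** The concern holds and should be fixed. The endpoint is clear, and the 50 participants follow from the plan's own inputs; what is missing is the analysis that decides Aim 1. If the VAS sentence is taken literally, the stated 80% power does not apply. At 25 per arm the group effect would have 10-14% power for a 2-hour-only benefit and 77-92% for a sustained one, and the group-by-time effect 67-91% for either. At 60 per arm the loss remains only for the group effect with a 2-hour-only benefit (19-26%). These figures are illustrations that rest on equal SDs, equal correlations of 0.3 to 0.6 and complete data, none of which the documents state. The gap itself does not depend on them.

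**What to change.** State in section 7c one primary analysis for Aim 1: the difference in 2-hour VAS by ANCOVA on arm, baseline VAS and anesthesia-type stratum, in all randomized patients with a 2-hour score, analysed as randomized, with the estimate, 95% CI and a two-sided 0.05 test. Label the repeated-measures analysis over all times secondary, with the arm contrast at each time. A Wilcoxon test can stay as a named sensitivity analysis.

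Naming the two-sample 2-hour test as primary would be enough to end the ambiguity. ANCOVA is preferred because it uses data already collected: at 25 per arm it has 83-93% power if baseline and 2-hour VAS correlate at 0.3 to 0.6, and loses about one point if they do not correlate. That correlation is unknown. If allocation is run separately by site, site can be added.

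The cost is wording only, with no new data or patients, and the stated sample size of 50 stands on its own inputs. The change should be made before unblinding. The conflict between 50 and 120 patients and the handling of missed telephone interviews are separate matters.

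### Section 7c assigns VAS a repeated-measures analysis with no missing-data rule, although the primary aim and the sample size are a two-group comparison at 2 hours; run complete-case, it would drop recorded 2-hour values

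*Combined protocol and SAP*

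**What the plan says.** Section 2 (Objectives, Aim 1) defines the primary endpoint: "we will determine the mean difference in postoperative pain at 2 hours in the treatment group" compared with saline, on the VAS.

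VAS is collected five times. Section 4a has it completed on the day of surgery. Section 4b adds the rest: "PUF questionnaire and VAS will be repeated at 2 hours, 2 weeks, 6 weeks and 3 months postoperatively via a telephone interview". The abstract (section 1) intends all five to be used: "Bladder pain will be compared at baseline, 2 hours, 2 weeks, 6 weeks and 3 months using the Visual Analog Scale".

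Section 7c contains four relevant statements:
- Sample size: "we are planning this study with 50 participants", based on 2-hour means of 50.1 (SD 27.9) and 70.6 (SD 22.6), type I error 0.05 and power 80%.
- Continuous measures generally: "normally distributed data will be compared with Students t test", with a Wilcoxon test if not normally distributed.
- VAS specifically: "Visual analog pain scores will be compared using repeated measures of variance".
- Dropouts: "an intention to treat analysis will be performed for the participants who drop out prior to study completion".

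No mixed model, imputation or missing-data rule appears anywhere. Section 4c gives a different number of patients: "We will randomize 120 patients total".

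**The concern.** The analysis named for the primary variable is not matched to the primary question. Aim 1 asks about one time point, and the trial was sized for that time point. The only method tied by name to VAS is one for several time points, and section 7c does not say which of its terms or contrasts answers Aim 1.

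This matters for missing data. Sections 4a and 8b place the patient in monitored recovery during the first 2 hours, so the 2-hour score should be nearly complete. The three later scores depend on telephone contact over 3 months. In its common complete-case form, a repeated-measures ANOVA keeps only patients with a value at every time. A patient with a valid 2-hour score could then leave the primary comparison because of a call missed weeks later. She is exactly the patient the intention-to-treat sentence is meant to protect.

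Two things are at stake: power, because the 50-patient plan has no allowance for loss, and a primary result that depends on who answers the telephone.

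**Working it through.** **1. Reproduce the plan's sample size.** Inputs from section 7c: difference 70.6 − 50.1 = 20.5 mm; pooled SD = √((27.9² + 22.6²)/2) = 25.39 mm; alpha 0.05, taken as two-sided; power 80%.

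n per arm = 2 × (1.960 + 0.842)² × 25.39² / 20.5² = 24.1, rounded up to 25, so N = 50. This matches. A one-sided test gives 38 and does not. The match is to a two-group comparison at 2 hours with no dropout allowance and no repeated-measures term.

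**2. Power if every 2-hour value is used.** Two-sample t test (noncentral t):
- 25 per arm: standard error 25.39 × √(2/25) = 7.2 mm, power 79.9%.
- 60 per arm (the 120 of section 4c): power 99.2%.

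**3. Power if patients with an incomplete series are dropped.** The documents give no dropout rate, so the rates below are assumptions. Loss is random. The number kept in each arm is binomial, and power is averaged over it.

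| Incomplete series | N = 50 | N = 120 |
|---|---|---|
| 0% | 79.9% | 99.2% |
| 10% | 75.2% | 98.6% |
| 20% | 69.8% | 97.4% |
| 30% | 63.4% | 95.3% |

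These figures are for the 2-hour contrast in the patients kept, which simplifies the full ANOVA.

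**4. How quickly incomplete series build up.** If each of the three later calls is missed independently with probability p, the incomplete proportion is 1 − (1 − p)³.
- p = 5%: 1 − 0.95³ = 14.3%, about 7 of 50; power at N = 50 about 73%.
- p = 10%: 1 − 0.90³ = 27.1%, about 14 of 50; power at N = 50 about 65%.

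**5. Bias, one illustration.** Suppose that in both arms 5% of patients scoring at or below 54 mm (the limit for severe pain in section 7a) and 30% of those above it are lost. With normal scores and z = (54 − mean)/SD, the completer mean is mean − 0.25 × SD × φ(z) / proportion kept, where 0.25 = 0.30 − 0.05.
- Lidocaine: z = 0.140, φ(z) = 0.395, proportion kept 0.839; 50.1 − 0.25 × 27.9 × 0.395/0.839 = 46.8.
- Saline: z = −0.735, φ(z) = 0.305, proportion kept 0.758; 70.6 − 0.25 × 22.6 × 0.305/0.758 = 68.3.

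The difference is 21.5 mm instead of 20.5 mm, a shift of 1.0 mm against a standard error of 7.2 mm. Loss that follows a different rule in each arm cannot be sized from the documents.

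**The case against.** A reader might infer that section 7c necessarily deletes anyone who misses a call, so that the plan contradicts itself. The documents do not support that. They nowhere exclude incomplete patients, and the VAS sentence fixes neither the model nor the time points. It could mean a mixed model, or an analysis of baseline and 2 hours only. Nor is deletion inherent in repeated-measures ANOVA: in a simulated set of 50 patients at five times with one late value removed, a univariate ANOVA with patient, time and time-by-arm terms used all 249 remaining values.

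The sentence on continuous measures could also be read as covering the 2-hour VAS, leaving repeated measures for VAS over time. Aim 1, the sample size and the intention-to-treat sentence all fit that reading.

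Finally, the power loss rests on assumed rates and is negligible at N = 120, and the illustrated bias is small.

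All of this stands, and it limits the point to a conditional one. It does not remove it. Section 7c names general tests and then gives VAS a separate method, so the favourable reading has to be supplied by the reader. The abstract points to all five times. If several analyses fit the text, some keeping these patients and some not, the primary analysis is not pre-specified.

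**Conclusion.** The point holds in conditional form. Section 7c does not match the VAS analysis to the 2-hour question for which the trial was sized, and it does not say how patients with missing calls stay in. If the analysis is run complete-case over all five times, recorded 2-hour values are discarded, in conflict with the intention-to-treat sentence.

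The cost in power is about 5, 10 or 17 percentage points at N = 50 for assumed incomplete rates of 10%, 20% or 30%. It matters only if N = 50 applies. The conflict between 50 and 120 patients is a separate matter that the sponsor must also reconcile. A reader might also infer serious bias; the documents do not show it. Under a common loss rule the illustrated shift is 1.0 mm, although loss differing by arm would remain a risk at either sample size.

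The change is worth making before any unblinded analysis, because it costs almost nothing and settles the primary test.

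**What to change.** In section 7c, replace the VAS sentence with:

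> The primary analysis compares 2-hour VAS between arms as randomized, with the t test or Wilcoxon test named above, using every recorded 2-hour value whether or not later calls are completed. Participants with no 2-hour VAS are counted and reported by arm, and a sensitivity analysis with imputed values is given. VAS over time is a secondary analysis by linear mixed model using all recorded values.

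Replace the intention-to-treat sentence with a definition of the set:

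> The intention-to-treat set is all randomized participants in their assigned arm, including those who later withdraw or are removed. Data already collected are kept.

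Section 4f needs no change for this purpose. The cost is wording in section 7c and slightly more analysis work (the mixed model and the imputation sensitivity analysis). The primary tests are already named there, and no further patients or measurements are needed.
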